7.2.1 Objectives

In the three collaborator hospitals we will:

- Report the proportion of women meeting each of the new criteria and in total in WS2 retrospective datasets – comparing these proportions relative to the hospital populations with published rates for our individual criteria. Where the criteria definitions appear to under or over-capture events, we will undertake record review to inform definition adjustment where required (approximately 10 case records per event of over/under capture).
- Undertake validation of the coded criteria through examining a stratified random sample of 100 sets of records of these cases across the three sites to assess whether the codes used in the electronic data correctly identified the conditions – again if necessary, allowing criteria definition adjustment.
- Review hospital systems for recording serious events in the time period, reviewing cases identified as maternal serious incidents (maternal serious incident cohort) but not identified by our criteria to establish whether criteria definition adjustment is required.

From MBRRACE-UK we will report the proportions of women who meet the new definitions.

- Learning will be fed back to the expert panel to generate final definitions.

Further details of the statistical analyses related to workstream 1 are given in Section 11.2.1.

7.2.2 Permissions and data flow

For both retrospective case record reviews detailed above we will need to review specific (uncommon) cases of adverse events in each of three hospitals, precluding individual consent. An application to the Confidential Advisory Group will be made (see Section 9.1.2 for further details).

[figure not shown]

Figure 1 Overview of Workstream 1

7.3 Workstream 2

Workstream 2 will, in collaboration with the NIHR Health Informatics Collaborative, develop an eight- to twelve maternity unit dataset. Current MOEWS' ability to identify newly defined 'near-miss' and 'pre-near-miss' events will be assessed using this data and data from the MBRRACE-UK dataset.

7.3.1 Identification of existing MOEWS

Existing MOEWS will be identified by updating an existing systematic review (see WS3a for methods) along with checking with experts in the field (11), and will include Irish, Scottish and American published tools along with the new NHSE/I tool (11,48–50).

7.3.2 Workstream 2a

We will curate retrospective datasets from routine NHS maternity unit electronic data to encompass the work in section 2b and 3b. Data will encompass variables required for prediction and data required for maternal and neonatal outcomes (to allow assessment of the predictive ability of the scores for adverse neonatal outcomes). For data types see section 12.1.2.

The output of this workstream will be the external validation performance of existing MOEWS. Details of the methods that will be used to carry this out are reported in Section 11.2.2.

7.3.2.1 Data collection and data flow

Retrospective whole maternal unit data from available electronic patient records for multiple sites is required (see statistical analysis) precluding individual patient consent. Databases will be built by automated electronic extraction with manual augmentation (including from paper records) where necessary. All data will be pseudonymised prior to analysis by the study team. An application to the Confidential Advisory Group will therefore be made to undertake this work (see Section 12 for further detail). A data flow diagram is included in the study documentation.

7.3.3 Workstream 2b

7.3.3.1 Participants

MBRRACE-UK undertakes confidential enquiries into maternal deaths and specific severe morbidities. We have already extracted event and vital sign data for 205 women who died or suffered severe morbidity (from pulmonary embolism and severe haemorrhage). In this work stream, we will additionally extract available re-laparotomy (n=32) and diabetic ketoacidosis cohorts (n=80) to complete representation of the available major reversible events. We will also extract additional outcome data to define when women meet the new 'near-miss' and 'pre-near-miss' criteria (WS1). This will require an extended output request to the Healthcare Quality Improvement Partnership. All women in the cohort are likely to have had one of the near-miss or pre-near-miss events (as defined in WS1) or death.

7.3.3.2 Data collection and data flow

We aim to replicate the data in WS2a. Anonymised data will be collated into research datasets onto University of Oxford secure servers where the MBRRACE dataset already resides. In the case of thromboembolism and major haemorrhage datasets, these have already been curated, but will require addition of pre-near-miss events and times as defined in WP1.

7.3.3.3 Outcome measures

The primary outcome for MOEWS assessment for both data sources (WP2a&b) will be a combination of maternal death, 'near-miss' and 'pre-near-miss' events (as defined in WS1). Secondary outcomes will be maternal death, 'near-miss' and 'pre-near-miss' events, individually. For more details on the analysis methods see Section 11.2.3.

7.4 Workstream 3

Workstream 3 will develop an eMOEWS candidate variable list by literature review informing a further Delphi process. An optimal vital-signs MOEWS and a multivariable eMOEWS will be developed and validated, exploring regression models and machine learning (ML) approaches.

7.4.1 Workstream 3a – developing the candidate variable list

7.4.1.1 Systematic review

We will undertake a systematic review and critical appraisal of routinely collected, electronically available variables which affect the risk of sustaining a 'near-miss' or 'pre-near-miss' event as defined in WS1. This will include noting key interactions between variables. We will include existing prediction models and associated publications. We will follow guidance by the Cochrane Prognosis Methods Group (51,52). We will search bibliographic databases including MEDLINE and EMBASE. We will snowball to identify any further relevant studies. Searches will be developed with an academic librarian (with whom we have previously worked). The literature between 01/01/1993 and 30/06/2023 will be identified without language restrictions. Data will be extracted in duplicate. Authors will be contacted by e-mail where additional information is required.

7.4.1.2 Review strategy

We will undertake quality assessment of included studies, where possible using the QUIPS tool for prognostic factors, recommended by the Cochrane Handbook for the appraisal of studies of risk factors (53,54). The piloted data extraction form will follow the prognostic factors adaptation (CHARMS-PF) of the Critical Appraisal and Data Extraction for Systematic Reviews of Prediction Modelling Studies

(CHARMS) guidance (52). We will further synthesise available data using a semi-quantitative method previously described by Zaal et al. (55) and adapted by Dettmer et al (56).

7.4.1.3 *Delphi strategy*

We will assess the variables identified during our systematic review against those recorded in our partner maternity sites to inform availability for inclusion. We will use this information to inform a 3-round international Delphi process to compile a list of existing, electronically available variables which affect the risk of 'near-miss' and 'pre-near-miss' events (as defined in WS1). This will generate a candidate variable list. Our strategy will follow a similar process to that in WS1.

The Delphi participants will again be identified from author lists of articles included in our review of the literature to ensure diverse expertise and selection objectivity. We will also involve our PPI colleagues. In round one, variables identified from our literature review will be presented to the Delphi participants along with their purported effect on risk (protective vs predisposing). To provide structure, variables will be grouped into a small number of domains including but not limited to demographics, vital signs, and laboratory variables. Participants will again be asked to identify any variables felt to be important but not included, and whether these are felt to represent protective factors or predisposing factors. Round 1 results will then be collected and curated by a Delphi facilitator.

Subsequent rounds will follow the processes described in WS1.

The final candidate variable list will then be assessed against availability in the 8-12 sites followed by data extraction of available candidate variables as part of WS2a. For likely variable types see section 12.1.2.

7.4.2 Workstream 3b – developing an optimal vital-signs MOEWS and multivariable eMOEWS

We will develop and externally validate (see Section 11.2.4 for further details):

- A vital-signs-based MOEWS for use in environments where connection to an EPR is not available.
- A multivariable electronic maternal early warning score (eMOEWS) for use in digitally mature environments

We will extract a separate, more recent 2-year validation cohort from eight-twelve sites to allow external validation (containing relevant variables) of the optimal vital-signs MOEWS and multivariable eMOEWS.

7.5 Workstream 4

In Workstream 4 we will:

- Build working eMOEWS web interfaces following user-centred design principles (Workstream 4a).
- Develop escalation and response pathways for women identified as at risk by the eMOEWS (Workstream 4b)

7.5.1 Workstream 4a

7.5.1.1 *Requirements identification*

To ensure a bespoke eMOEWS user interface we will undertake evaluation of end-user needs for user interfaces using focus groups, with topic guides underpinned by Normalisation Process Theory and informed by the NASSS framework to identify barriers and facilitators, local adaptions and unintended consequences influencing implementation and hence potential effectiveness across the implementation sites. We aim to conduct 2-3 focus groups with up to 20 professionals per site (we anticipate this number will allow representation of the views of a range of professionals of different seniority – but will continue focus groups until saturation has been achieved).

7.5.1.2 *Interface design*

We will develop the key design elements and functionality for the web-interface through work including Applied Cognitive Task Analysis Interviews (57) with multi-disciplinary staff (including obstetricians, midwives and anaesthetists) and “card sorting” (58) exercises in implementation sites (59) to prioritise categories of information (e.g., demographics, vital signs, laboratory tests, eMOEWS risk score) displayed in the interface. We estimate approximately thirty cross-implementation site meetings with clinical staff will be required but will continue until no major new information is being obtained.

After installation of the eMOEWS system, we will trial the user interface with key stakeholders. We will encourage staff to use the eMOEWS to display information from patients currently under their care. As clinicians are likely to be familiar with these patients’ recent clinical data, we will use this to discover minor omissions and local adaptions that could be addressed to enhance the system. We will continue trials until saturation occurs – but again estimate around 30 meetings with key stakeholders across sites. Learning from eMOEWS use within WS4b will also be iteratively incorporated into the final interface. We will document the time and equipment consequences of eMOEWS installation and maintenance at each site and centrally to inform WS5c.

Testing metrics will include task-based efficiency and effectiveness, user satisfaction and workload.

7.5.2 **Workstream 4b**

We will develop escalation pathways using:

- Secondary analysis of interviews with women who experienced near-miss morbidity.
- Interviews with women and partners who have recently experienced maternity complications.
- Focus groups
- A response pathway co-design group.

We will conduct secondary analysis of interviews with 36 women who experienced near-miss morbidity and 11 of their partners who were interviewed through the ‘healthtalk’ series (Health Experiences Research Group) to capture women and partners’ perspectives relating to the recognition and management of acute illness in a maternity setting.

In addition, we will conduct a further 10-15 interviews or focus groups with women and partners from diverse groups who have recently experienced maternity complications to ensure we are capturing any specific barriers identified amongst women from diverse ethnic groups and amongst those who are vulnerable. Costs for translation services during these interviews (where required) are included in the budget. We will identify participants using posters in our partner hospitals and through our contacts with

trusted community support and patient groups. To maximise participation, we will offer a choice of online and face-to-face interviews and accessible community venues. A topic guide for interviews will be developed from previous work and secondary analysis of interviews above. Additional semi-structured questions will be asked, using a topic guide. A list of questions will be submitted as a study amendment prior to interviews/focus groups commencing.

Consensus best practice MOEWS responses to the NHSE/I MOEWS have been identified through a Delphi process using example clinical scenarios conducted by the co-applicant team with NHSI. These, with other published response pathways (3), and findings from our interviews, guided by Normalisation Process Theory underpinned by key NASSS domains, will inform topic guide content for focus groups, to identify barriers and facilitators, local adaptions and unintended consequences influencing response implementation and effectiveness.

We will apply inter-related social and behavioural science theories and frameworks to address the individual, socio-cultural and organisational factors influencing escalation responses. We will particularly explore factors influencing decision making and intentions around whether or not to escalate, and factors influencing appropriate and timely response as failure to escalate and respond appropriately could influence the effectiveness of the eMOEWS to prevent deterioration. Following the Behaviour Change Wheel approach to intervention design (60), we will use the findings from this behavioural analysis as a basis for systematically co-designing a response pathway to target the key factors facilitating or hindering escalation on the basis of an eMOEWS trigger in this context.

Response pathway co-design will then be undertaken with relevant stakeholder group representatives (e.g., pregnant women, healthcare professionals, experienced mMOET course leaders – see below – again including translation where necessary) paying particular attention to information from women whose voices and concerns find it harder to be heard and responded to (61,62). Key staff from intervention sites will be involved in escalation pathway development, ensuring a core intervention applicable across sites (and across the NHS), and identifying minor adaptions outside the core intervention to allow individual site integration. We will focus on minimising the perceived opportunity costs of implementation, working with the focus groups and local champions to foster the internal (within NHS) view (63,64). We envisage two meetings will be required with preparation work undertaken prior to each meeting, with initial pathways designed by the research team between meetings.

7.5.3 Workstream 4c

The research team will develop three simulated scenarios informed by the brief clinical scenarios used for development of the NHSE/I National MOEWS. These will be designed to refine the clinical escalation and response pathways developed in WS4b for representative near-miss and pre-near-miss events. Local champions from intervention sites will be involved in scenario development and manualisation of the escalation pathway to ensure that the core intervention remains applicable across sites (and across the NHS) and that minor adaptions outside the core intervention allow individual site integration. We will then run and record scenario simulations at four mMOET training centres, building on pre-existing scenarios (e.g. post-partum haemorrhage and sepsis). Simulations will include a mixture of medical staff and midwives at representative levels of experience (8 in each of the implementation sites). Findings will inform escalation protocol review prior to repeat (potentially adjusted) scenario testing.

From our prior experience of this process, we estimate two iterations with decreasing participant time will be required to finalise recommended escalation protocols.

8 PARTICIPANT IDENTIFICATION

8.1 Study participants

8.1.1 Patient Retrospective cohort

All women who are treated by maternity services at study sites.

8.1.1.1 Overall Inclusion criteria

- All women aged 16 or over who are pregnant
- At any of the study sites

8.1.1.2 Overall Exclusion criteria

- Patients who have requested that their data not be used for research (e.g., NHS Opt-out, see Section 9.3.1)

The model development dataset sits within this cohort.

The case review dataset sits within this cohort. We will extract a stratified sample of 100 records for case review identified by our new criteria. The case review data set will comprise records:

- At one of three partner sites
- Electronically coded to meet a pre-near-miss/near-miss criterion.

The maternal serious incident dataset sits within this cohort. We will review up to 100 maternal serious incidents recorded in local serious event systems at the three partner hospitals not identified by our new electronic criteria. The maternal serious incident data set will comprise records:

- At one of three partner sites
- Not electronically coded to meet a pre-near-miss criterion.
- Recorded in local serious incident reporting systems.
- With a clinical rather than “operational” serious incident

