| | To assess performance of the new near-miss and pre-near-miss outcome criteria in 3 hospitals and MBRRACE-UK in: 
 • a stratified random sample of 100 sets of records of near-miss and pre-near-miss cases across the three sites. • clinical serious maternal events recorded in hospital serious event systems. • MBRACCE-UK cases | Descriptive statistics to describe whether the electronic criteria used correctly identified the conditions. Descriptive statistics of missed and captured events according to electronic criteria Descriptive comparison to published rates | During pregnancy or in the immediate postpartum period. |
| | To develop a large representative eight to twelve maternity unit cohort for model development and assessment | Cohort developed and ready for assessment | 05/2029 |
| | To investigate the performance of existing MOEWS/MEWS in the new maternity cohort and in women who have died or had a near-miss or pre-near-miss event in pregnancy | Evidence-based assessment of existing MOEWS, both in new retrospective (assessed by discrimination, risk of our key events at each MOEWS/MEWS level) and nationally recognised mortality/morbidity (assessed | 05/2029 |

| | | | |
|--|---|---|---------|
| | | by sensitivity and duration of prior warning) cohorts | |
| | To develop and validate an optimal vital-signs-only-based MOEWS | Relative performance of new MOEWS, best published MOEWS and NHSI national MOEWS for prediction of near-miss or pre-near-miss | 05/2029 |
| | To develop and validate an eMOEWS to improve detection in comparison to existing MOEWS/MEWS | Relative performance assessment of eMOEWS, new validated vital-signs-based MOEWS, best published MOEWS and NHSI national MOEWS for prediction of 'near-miss' or 'pre-near-miss' | 05/2029 |
| | To design and deliver an eMOEWS interface | User co-designed eMOEWS implemented within 4 NHS sites. System Usability Scale performance | 05/2029 |
| | To develop treatment escalation pathways | Escalation and response pathways protocolised iterated and tested in a simulated environment | 05/2029 |

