9.2 Screening and Eligibility Assessment

9.2.1 Patients

- Retrospective and prospective cohorts - there will be no screening in this study.
- Case review cohort – a stratified random sample of cases for review will be computer-generated from each of three partner sites using WP2 pre-anonymisation datasets (post application of the NHS opt-out and patients who have made requests to study sites for their data to be excluded).
- Maternal serious incident cohort – serious incident databases at partner hospitals will be screened for women with clinical maternal serious incident reports.

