11.2 Description of the Statistical Methods

11.2.1 Workstream 1

We will report descriptive statistics describing the proportion of women meeting each of the new criteria and in total in WS2 retrospective datasets – comparing these proportions relative to the hospital populations with published rates for our individual criteria,

We will use descriptive statistics to report the proportions of events correctly captured by our new electronic definitions in the stratified sample cohort and events missed in our review of hospital systems for recording serious events.

Similarly, from MBRRACE-UK we will report the proportions of women who meet the new definitions.

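### The two hospital review datasets give a positive predictive value and a list of missed incidents, but no proportion of events captured or missed

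*Protocol*

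**What the plan says.** Protocol section 8.1.1.2 defines two review datasets within the retrospective cohort at three partner hospitals.

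- **Case review:** "We will extract a stratified sample of 100 records for case review identified by our new criteria". The listed condition is "Electronically coded to meet a pre-near-miss/near-miss criterion".
- **Maternal serious incidents:** "We will review up to 100 maternal serious incidents recorded in local serious event systems". The lead-in sentence limits these to incidents that the new criteria did not identify, and the matching bullet reads "Not electronically coded to meet a pre-near-miss criterion".

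Section 11.2.1 says the analysis will "report the proportions of events correctly captured by our new electronic definitions in the stratified sample cohort and events missed in our review" of hospital serious-event systems. The synopsis lists as an outcome measure "Descriptive statistics of missed and captured events according to electronic criteria", and section 6 repeats it.

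Section 7.2.1 gives the purposes. The 100 records test whether the codes identify the conditions correctly. The incident review takes cases reported as serious incidents "but not identified by our criteria to establish whether criteria definition adjustment is required".

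Section 9.2.1 describes a wider screening step: "serious incident databases at partner hospitals will be screened for women with clinical maternal serious incident reports". Section 11.2.1 also plans to report the share of MBRRACE-UK women who meet the new definitions.

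**The concern.** A proportion of events captured needs true events in its denominator, some flagged and some not. Neither hospital dataset has that mix, because each admits only one result of the criteria being assessed. A reader of section 11.2.1 would take the 100-record result for a capture rate when it measures something else, and the incident review would show every case as missed because of how it was assembled.

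The definitions matter downstream. With maternal death they form the composite primary outcome for assessing existing scores (section 7.3.3.3), and they are the events that the new scores are to predict (section 6). An event that the criteria miss is treated as a non-event in those analyses, so the share missed among hospital cases is worth knowing.

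**Working it through.** The protocol gives no precision calculation for these two datasets, so there is no figure to reproduce. The check is which proportion each sampling rule can identify.

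**Notation.** Among hospital records, let *a* be true events that are flagged, *b* flagged records that are not true events, and *c* true events that are not flagged.

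- Positive predictive value = a / (a + b)
- Proportion captured = a / (a + c)
- Proportion missed = c / (a + c)

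**Case review (100 records, all flagged).** Records come only from *a* and *b*, so the share confirmed estimates a / (a + b). No record from *c* can enter, and a / (a + c) is not available. The positive predictive value itself is estimable. The Wilson 95% interval, with k = 1.96, is

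[p + k²/2n ± k√(p(1−p)/n + k²/4n²)] / (1 + k²/n).

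With n = 100 and assumed values of p, 80% confirmed gives 71% to 87%, and 90% confirmed gives 83% to 95%. These are unweighted. The sample is stratified, so an overall figure needs stratum weights.

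**Serious incidents (up to 100, all unflagged).** Within the dataset, captured is 0 of m and missed is m of m, whatever the true performance. Let T be all clinical serious incidents screened, flagged or not. Capture among them is 1 − m/T. The protocol does not give T, so the values below are assumptions, with m = 100 taken from the stated cap:

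| T (assumed) | Capture, 1 − 100/T | Wilson 95% CI |
|---|---|---|
| 100 | 0% | 0% to 4% |
| 150 | 33% | 26% to 41% |
| 200 | 50% | 43% to 57% |
| 300 | 67% | 61% to 72% |
| 500 | 80% | 76% to 83% |
| 1,000 | 90% | 88% to 92% |

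The same 100 records fit every row. If more than 100 incidents are unflagged, the cap also hides the full number missed.

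**Pooling the two.** The sizes are set by design, so a ratio across the datasets is not a capture rate. If 90 of the 100 flagged records were confirmed, 100 reviewed incidents would give 90/(90 + 100) = 47% and 20 would give 90/(90 + 20) = 82%. The ratio follows the number reviewed.

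**MBRRACE-UK.** These women were not selected on the new criteria, and section 7.3.3.1 expects that all are likely to have had a qualifying event or died. The share meeting the definitions is therefore a capture proportion, but for deaths and selected severe morbidity only.

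**The case against.** The case on the other side is substantial.

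- **The 100-record sample suits its purpose.** Section 7.2.1 asks whether the codes identify the conditions correctly, and the synopsis and section 6 list a matching outcome. A flagged-only sample is the right design for that. This stands; the fault is in section 11.2.1's label.
- **The missed events may be meant as a count.** The sentence in section 11.2.1 can be read that way, and close reading of unflagged incidents serves the aim of adjusting definitions. This stands as a reading, but a count alone says nothing about how often the criteria miss.
- **The denominator is within reach.** Section 9.2.1 screens for all women with clinical reports, and an incident can be called unflagged only after checking it against the criteria. This is true, and it is why the fix is cheap. No section commits to keeping or reporting the flagged number. The SAP, which is not at hand, might add it, but the protocol's dataset definition leaves flagged incidents out.
- **There are other checks.** MBRRACE-UK gives capture at the severe end. Section 7.2.1 also compares criterion rates with published rates and reviews records where they diverge. That comparison is indirect, because false positives and misses can offset each other.
- **The bullet's omission of near-miss is a slip.** Taken alone, it would let a record coded only as near-miss count as missed. The lead-in sentence and section 7.2.1 refer to the criteria as a whole and govern, so the documents do not support reading it as an intended rule.

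**Conclusion.** The point holds in a limited form. As section 8.1.1.2 defines them, the two hospital datasets yield a positive predictive value and a list of unflagged incidents. They yield no proportion of events captured or missed, although section 11.2.1 and the listed outcome point to one. Capture among hospital-reported incidents has no denominator.

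A reader might infer that captured and missed events cannot be estimated at all, or that the study has no means of learning how often the criteria miss events. The documents do not support that. The 100-record sample answers its own question, a count of misses is available, MBRRACE-UK covers severe cases, and planned screening could supply the total.

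The range of 0% to 90% capture for 100 unflagged incidents rests on assumed totals of 100 to 1,000. It shows what the dataset leaves open and does not predict performance.

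**What to change.** 1. In sections 8.1.1.2 and 11.2.1, state that every clinical maternal serious incident screened at the three sites will be classified as flagged or unflagged by any near-miss or pre-near-miss criterion. Report flagged/total with a 95% confidence interval.
2. Describe that figure as capture relative to locally reported serious incidents, under the version of the criteria tested. Local reporting does not cover all true events, and section 7.2.1 allows the definitions to change afterwards.
3. Keep detailed review for unflagged incidents. If there are more than 100, review a random sample and report the full unflagged count.
4. In section 11.2.1, call the 100-record result a positive predictive value, weighted by stratum for any overall figure.
5. Reword the bullet to: *not coded to meet any near-miss or pre-near-miss criterion*, in line with its lead-in sentence.

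The cost is protocol wording and a small tally. Each screened incident must already be classed to apply section 8.1.1.2, and flagged incidents need no extra record review.
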